2.4 Study Design

For clinicaltrials.gov and Stanford Clinical Trials Directory compliance

This is a pilot, single-center study in subjects with liver tumors. The primary objectives of this prospective pilot study is to (1) determine the feasibility and reproducibility of 3D contrast

enhanced ultrasound imaging in liver cancer patients undergoing Stereotactic Ablative Radiotherapy and (2) evaluate whether there are treatment induced early changes in imaging metrics derived from 3D contrast enhanced ultrasound. This study will provide valuable insight as to the potential of baseline and/or early post-treatment 3D ultrasound perfusion characteristics (measurements of blood-flow) of primary and metastatic liver tumors to predict tumor response to Stereotactic Ablative Radiotherapy.

The target lesion will be located at the simulation CT scan for treatment planning. Prior to Definity® administration, gray scale and Doppler (color or power imaging) ultrasound investigations of the target lesion will be performed using commercially available ultrasound equipment and standard techniques (B-mode or Harmonic imaging) to study the anatomy of the target lesion and surrounding parenchyma.

Immediately after the unenhanced ultrasound evaluation, contrast-enhanced ultrasound will be performed, according to the procedures described to study the lesion vascularity in comparison to the surrounding parenchyma. Definity® will be administered intravenously through a central line or in a peripheral vein.

Unenhanced ultrasound and Definity®-enhanced ultrasound images will be recorded and stored anonymously.

The primary analysis will be based on comparison of the readout (perfusion parameters of the lesion) at baseline, at 0-7 days after the first fraction of radiotherapy treatment, 2-4 months following the start of radiotherapy, and the clinical outcome of the patient, including findings on routine CT and PET-CT imaging.

This is a Single Group, Open Label Study designed to evaluate to evaluate as a primary outcome feasibility and efficacy.

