10.1.4 Measurement Time Points

The probe will be held steady throughout each acquisition. During the infusion, continuous 3D data will be collected and two disruption-replenishment acquisitions will be performed.

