10.1.5 Image analysis and derived measures

Volume of interest (VOIs) encompassing the lesions will be defined on the 3D DCE-US. After linearization of the 3D DCE-US signal (to make it proportional to contrast concentration), time intensity curves (TIC) will be generated for the mean contrast concentration within the VOI. After standard TIC fit curve parameters will be extracted to serve as measures that describe perfusion. These measures include: relative blood volume, mean flow velocity, and relative blood flow = relative blood volume x mean flow velocity.

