12 STATISTICAL CONSIDERATIONS

12.1 Statistical Design

The primary objectives of this pilot study is to (1) determine the feasibility and

reproducibility of 3D contrast enhanced ultrasound imaging in liver patients undergoing Stereotactic Ablative Radiotherapy and (2) evaluate whether there are treatment induced early changes in imaging metrics derived from 3D contrast enhanced ultrasound. Specifically, we will perform exploratory analysis for testing the following hypotheses:

12.2 Outcome Measurements:

Primary endpoints:

- To characterize the reproducibility of 3D DCE-US by estimating the concordance correlation coefficient (30,31) for repeated 3D DCE-US measures (see Section 10.1.6, Image analysis and derived measures).
- To determine the variance in the relative changes of repeated 3D DCE-US measures.
- To provide summary statistics of the relative changes in 3D DCE-US measures before and after SABR.

Secondary endpoint:

- To provide relative number of 3D DCE-US examinations in which fusion to CT is possible with tracking of the ultrasound transducer.

12.3 Analysis plan:

This is an exploratory pilot study designed with a primary objective to evaluate (1) the feasibility and reproducibility of 3D DCE-US in cancer patients undergoing SABR for liver lesions and (2) the magnitude of the differences in perfusion measures before and after SABR. Future studies will seek to understand if 3D DCE-US perfusion baseline values or changes have predictive power for clinical endpoints in SABR treatments. The knowledge gained from this study will aid in calculating the appropriate sample size for such studies. The main focus here is on understanding the discrepancies in measures from repeated acquisitions and differences in measures before and after SABR. Thus the data will be analyzed as follows:

- Estimation the concordance correlation coefficient (30, 31) for repeated 3D DCE-US measures (see Section 10.1.6, Image analysis and derived measures) as a measure of reproducibility. Concordance correlation values between 0.9 and 0.95 will be interpreted as moderate reproducibility and values between 0.95 and 0.99 will be interpreted as substantial reproducibility based on the following scale for the concordance correlation coefficient: Poor, < 0.9; moderate, 0.9 – 0.95; substantial 0.95 – 0.99, nearly perfect >0.99.

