- Histogram analysis and summary statistics (mean, median, variance, and maximum) of the relative changes (difference/average) of repeated 3D DCE-US measures. (Small variance and zero mean of the relative changes will be indicative of highly reproducible 3D DCE-US measures).
- Histogram analysis and summary statistics (mean, median, variance, and maximum) of the relative changes (difference/baseline) in 3D DCE-US measures before and after SABR. Large mean differences will be indicative of treatment (SABR) effect.

- Calculation of proportion of 3D DCE-US examinations in which fusion to CT is possible with tracking of the ultrasound transducer. Calculation of proportion of 3D DCE-US examination in which repeated scans is successful. These proportions are metrics of feasibility (target 80%-90%). Successful fusion to CT in particular is important metric is 3D DCE-US is to be explored as add-on imaging for treatment planning in further studies.

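### Section 10.1.5 does not mask the person defining the VOIs to visit, and does not say whether the two repeat acquisitions share one VOI or what the CCC then covers.

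*Combined protocol and SAP*

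**What the plan says.** All references are to the combined protocol and SAP.

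- **VOI step.** Section 10.1.5 gives the only rule: "Volume of interest (VOIs) encompassing the lesions will be defined on the 3D DCE-US". Next, "time intensity curves (TIC) will be generated for the mean contrast concentration within the VOI", and the fitted curve yields relative blood volume, mean flow velocity and their product, relative blood flow. No section says who defines the VOI, by what method, in what order scans are read, or whether the visit is visible. Sections 12.2 and 12.3 point to a section 10.1.6 under the title that 10.1.5 now carries; this looks like a misnumbering and adds no reading rule.
- **Repeats.** Section 10.1.4 says that during the infusion "two disruption-replenishment acquisitions will be performed" and "The probe will be held steady throughout each acquisition". A common VOI is neither required nor excluded.
- **Design.** Section 2.4: "This is a Single Group, Open Label Study". The nearest text to masking is in the same section: "ultrasound images will be recorded and stored anonymously".
- **Interpretation.** In section 12.3, CCC values from 0.9 to 0.95 "will be interpreted as moderate reproducibility"; below 0.9 is poor and 0.95 to 0.99 is substantial. For the comparison with baseline, "Large mean differences will be indicative of treatment (SABR) effect".

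**The concern.** The VOI feeds every primary perfusion measure, so any habit in how it is defined passes straight into the results. Two separate gaps follow.

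**Before/after change.** Someone who knows that a scan is post-SABR may, without intending it, place the boundary differently from baseline. There is no control group in which the same drift would show up, and the plan attributes a large mean change to SABR. Recruiting more patients would not remove such a bias.

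**Reproducibility.** If both repeats use one VOI, the error of defining it is common to the pair and cancels. Scans from different visits are separate examinations, so that error does enter the before/after change. The CCC band, and the variance of the repeat differences (also a primary endpoint), would then describe less than the whole measurement. Section 12.3 says the results will help to size later studies, so the omission could carry forward.

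**Working it through.** The plan has no calculation to reproduce: section 12.4 gives 20 patients, and section 12.5 says there is too little information for a sample size calculation. The figures below are illustrations from assumed inputs.

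**1. CCC with independent and shared VOIs**

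Assumed proportional errors: between-patient b = 0.50, acquisition a = 0.10, VOI definition v = 0.05 to 0.15.

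- Independent VOIs: CCC = b² / (b² + a² + v²)
- Shared VOI: CCC = (b² + v²) / (b² + v² + a²)
- Gap: v² / (b² + a² + v²)

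| v | Independent | Shared | Gap |
|---|---|---|---|
| 0.05 | 0.25/0.2625 = 0.952 (substantial) | 0.2525/0.2625 = 0.962 (substantial) | 0.010 |
| 0.10 | 0.25/0.27 = 0.926 (moderate) | 0.26/0.27 = 0.963 (substantial) | 0.037 |
| 0.15 | 0.25/0.2825 = 0.885 (poor) | 0.2725/0.2825 = 0.965 (substantial) | 0.080 |

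Over b = 0.40 to 0.60, a = 0.08 to 0.10 and v = 0.10 to 0.15, the gap runs from 0.01/0.38 = 0.03 to 0.0225/0.1889 = 0.12.

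In a simulation of 20 pairs (40,000 runs; b = 0.50, a = 0.10, v = 0.10), the estimated CCC reached 0.95 in 16% of runs with independent VOIs and 71% with a shared VOI.

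**2. Variance of the repeat difference**

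Shared: 2a² = 0.02, so SD = 0.14. Independent: 2(a² + v²).

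- v = 0.05: 0.025, ratio 1.25
- v = 0.10: 0.040, ratio 2
- v = 0.15: 0.065, SD = 0.25, ratio 3.25

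**3. Before/after change when nothing has changed**

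For a measure of the blood-volume type, suppose a share f of the follow-up VOI is replaced by tissue with relative perfusion k. The apparent change is (1 − f) + fk − 1 = f(k − 1).

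- k = 0.5, f = 5% to 20%: −2.5% to −10%
- k = 2, f = 5% to 20%: +5% to +20%

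For scale, the 95% half-width of a mean change in 20 patients is 2.093 × SD/√20: about 9%, 14% and 19% for assumed SDs of 20%, 30% and 40%.

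**4. Reading load**

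With one target lesion per patient and all scans done: 20 × 3 = 60 examinations and 60 × 2 = 120 acquisitions. That is 60 VOIs if the repeats share one and 120 if they do not.

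**The case against.** The strongest reply concerns the repeats. The contrast-enhanced examination text in section 4 says the measurement is done twice to assess the reproducibility of the replenishment-curve analysis, and both acquisitions come from one infusion. For that purpose one shared VOI is a legitimate design, and the higher CCC is the right answer to a narrower question. This stands: someone reading the plan might infer that the CCC is inflated, but the documents do not support that. What remains is that section 12.2 presents the CCC as the reproducibility of 3D DCE-US without saying which error sources it covers.

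Three further points are fair.

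- The documents are silent. It is tempting to infer that VOIs will be hand-drawn by someone who knows the visit, or copied from one repeat to the other. Nothing says so; the supportable statement is that no rule is given. Anonymous storage does not settle it either way, because it concerns identity and not visit labels.
- No direction of bias is fixed. The analysis plan states no expected direction of change. Section 10.1.5 also places VOI definition before curve fitting and requires the VOI to encompass the lesion. Both limit steering towards a result, but do not exclude it.
- This is an exploratory pilot reporting summary statistics, with no formal test specified. That lowers the stakes. It does not remove the point, because the plan still attaches a treatment interpretation to the mean change.

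**Conclusion.** The concern holds in two parts. First, the plan has no masking to visit in an open-label, single-group study where a large mean change is read as a SABR effect. This holds whether or not the repeats share a VOI. Second, the plan leaves the shared-or-separate rule open, so the scope of the CCC and of the repeat variance is undefined.

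The mechanism follows from the documents; its size does not. Every variance component, and f and k, are assumed. With b = 0.50 and a = 0.10, a VOI CV of 5% moves the CCC by about 0.01 with no change of band, 10% moves it by about 0.04 and one band, and 15% by about 0.08 and two bands. A two-band shift should therefore not be taken as the expected case. This is an improvement the plan should make, not a defect that invalidates the pilot.

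**What to change.** Amend section 10.1.5 as follows.

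- The same reader defines all VOIs on scans that carry random codes, with the visit date removed, presented in random order.
- The target lesion is identified by its liver segment or planning-CT location, so that the same lesion can be found on coded scans.
- VOIs are defined without sight of any fitted values and are locked before the codes are broken.
- One of two rules for the repeats is declared. Either the paired VOIs are defined independently, each without sight of the other; or they share one VOI, and sections 12.2 and 12.3 state that the CCC and its bands describe acquisition and curve-fit repeatability only. Under the second rule, the repeat variance is not used alone to plan later before/after studies.

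The choice between these rules is a choice of what is being estimated, so it should be made explicitly.

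**Cost.** Coding and shuffling of stored scans, and up to 120 VOIs instead of 60 if the repeats are done separately. Masking will be imperfect where treatment change is visible on the image. No extra reader, scan or patient is needed.

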10.2 Secondary Outcome

In this pilot study of 20 patients, we will focus on the primary objective: feasibility, reproducibility and assessment of changes in metrics (indices) derived from 3D contrast enhanced ultrasound. Our secondary objective is to evaluate the feasibility of contrast-enhanced ultrasound-to-CT fusion by *assisting three-dimensional (3D) perfusion ultrasound (US) imaging with optical and electromagnetic tracking of the ultrasound probe* on patients with liver cancer that will undergo CT for treatment planning and/or response evaluation. Thus the secondary outcome will be the relative number of ultrasound examinations in which fusion to CT was possible.

11 REGULATORY CONSIDERATIONS

11.1 Data and Safety Monitoring Plan

The Stanford Cancer Institute Data and Safety Monitoring Committee (DSMC) will be the monitoring entity for this study. The DSMC will audit study-related activities to determine whether the study has been conducted in accordance with the protocol, local standard operating procedures, FDA regulations, and Good Clinical Practice (GCP). This may include review of the following types of documents participating in the study: regulatory binders, case report forms, eligibility checklists, and source documents. In addition, the DSMC will regularly review serious adverse events and protocol deviations associated with the research to ensure the protection of human subjects. Results of the DSMC audit will be communicated to the IRB and the appropriate regulatory authorities at the time of continuing review, or in an expedited fashion, as needed.

11.2 Data Management Plan

Case Report Forms (CRFs) are printed or electronic documents designed to record all protocol-related information on each trial participant. CRFs should summarize the clinical findings and observations necessary to ensure safety of participants on the study, and to document the study outcomes. CRFs are required by the SRC for all Interventional studies. Study-specific CRFs will document treatment outcomes for data analysis. CRFs will be developed manually and will be maintained by the study coordinator.

12 STATISTICAL CONSIDERATIONS

12.1 Statistical Design

The primary objectives of this pilot study is to (1) determine the feasibility and

reproducibility of 3D contrast enhanced ultrasound imaging in liver patients undergoing Stereotactic Ablative Radiotherapy and (2) evaluate whether there are treatment induced early changes in imaging metrics derived from 3D contrast enhanced ultrasound. Specifically, we will perform exploratory analysis for testing the following hypotheses:

12.2 Outcome Measurements:

Primary endpoints:

- To characterize the reproducibility of 3D DCE-US by estimating the concordance correlation coefficient (30,31) for repeated 3D DCE-US measures (see Section 10.1.6, Image analysis and derived measures).
- To determine the variance in the relative changes of repeated 3D DCE-US measures.
- To provide summary statistics of the relative changes in 3D DCE-US measures before and after SABR.

Secondary endpoint:

- To provide relative number of 3D DCE-US examinations in which fusion to CT is possible with tracking of the ultrasound transducer.

12.3 Analysis plan:

This is an exploratory pilot study designed with a primary objective to evaluate (1) the feasibility and reproducibility of 3D DCE-US in cancer patients undergoing SABR for liver lesions and (2) the magnitude of the differences in perfusion measures before and after SABR. Future studies will seek to understand if 3D DCE-US perfusion baseline values or changes have predictive power for clinical endpoints in SABR treatments. The knowledge gained from this study will aid in calculating the appropriate sample size for such studies. The main focus here is on understanding the discrepancies in measures from repeated acquisitions and differences in measures before and after SABR. Thus the data will be analyzed as follows:

- Estimation the concordance correlation coefficient (30, 31) for repeated 3D DCE-US measures (see Section 10.1.6, Image analysis and derived measures) as a measure of reproducibility. Concordance correlation values between 0.9 and 0.95 will be interpreted as moderate reproducibility and values between 0.95 and 0.99 will be interpreted as substantial reproducibility based on the following scale for the concordance correlation coefficient: Poor, < 0.9; moderate, 0.9 – 0.95; substantial 0.95 – 0.99, nearly perfect >0.99.
- Histogram analysis and summary statistics (mean, median, variance, and maximum) of the relative changes (difference/average) of repeated 3D DCE-US measures. (Small variance and zero mean of the relative changes will be indicative of highly reproducible 3D DCE-US measures).
- Histogram analysis and summary statistics (mean, median, variance, and maximum) of the relative changes (difference/baseline) in 3D DCE-US measures before and after SABR. Large mean differences will be indicative of treatment (SABR) effect.

- Calculation of proportion of 3D DCE-US examinations in which fusion to CT is possible with tracking of the ultrasound transducer. Calculation of proportion of 3D DCE-US examination in which repeated scans is successful. These proportions are metrics of feasibility (target 80%-90%). Successful fusion to CT in particular is important metric is 3D DCE-US is to be explored as add-on imaging for treatment planning in further studies.

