1 OBJECTIVES

1.1 Primary Objective

The primary objectives of this prospective pilot study is to (1) determine the feasibility and reproducibility of 3D contrast enhanced ultrasound imaging in liver cancer patients undergoing Stereotactic Ablative Radiotherapy and (2) evaluate whether there are treatment induced early changes in imaging metrics derived from 3D contrast enhanced ultrasound. This study will provide valuable insight as to the potential of baseline and/or early post-treatment 3D ultrasound perfusion characteristics (measurements of blood-flow) of primary and metastatic liver tumors to predict tumor response to Stereotactic Ablative Radiotherapy. Our underlying goal is to assess whether early perfusion changes at 0-7 days after SABR initiation can be used as a non-invasive early biomarker for treatment response assessment.

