During the unenhanced ultrasound examination, the morphology and localization of the target FLL will be evaluated using gray scale ultrasound and color/power Doppler modes. The target lesion will be identified using gray scale ultrasound and its location will be identified using Coineaud's system. Then, either color Doppler imaging or power Doppler imaging should be used to study the morphology/vascularity of the target lesion and surrounding parenchyma. Specific measurements with Spectral Doppler may be used depending on the presence and/or visualization of vessels.

Contrast-Enhanced Ultrasound Examination

The following protocol will be used, according to published literature (23):

An infusion of 1.3 mL of Definity diluted in 50 mL of saline will be administered using an injection pump. Two minutes will be allowed for the infusion to reach a steady level before disruption-replenishment. Measurements will be performed two times (to assess reproducibility of the replenishment curves analysis following microbubble destruction and replenishment of microbubbles into the US field-of-view).

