10.1.2 Measurement Definition

Primary Objective:

The primary objectives of this pilot study is to (1) determine the feasibility and reproducibility of 3D contrast enhanced ultrasound imaging in liver patients undergoing Stereotactic Ablative Radiotherapy and (2) evaluate whether there are treatment induced early changes in imaging metrics derived from 3D contrast enhanced ultrasound.

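### Section 12.3 reads a reproducibility label from a concordance correlation point estimate without an interval or named visits, and both repeats share one infusion, so the result is same-infusion repeatability

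*Combined protocol and SAP*

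**What the plan says.** The first primary endpoint in Section 12.2 is estimation of the CCC for repeated perfusion measures. Section 12.3 grades the value: poor below 0.9, moderate from 0.9 to 0.95, substantial from 0.95 to 0.99, nearly perfect above 0.99. In its words, "values between 0.95 and 0.99 will be interpreted as substantial reproducibility". Section 12 plans no confidence interval; the term appears only in the abbreviation list.

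The measures are listed in Section 10.1.5: "These measures include: relative blood volume, mean flow velocity, and relative blood flow". Sections 12.2 and 12.3 point to a Section 10.1.6 for them, but the section with that title is 10.1.5, and it does not define the pairs.

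A repeat is described in Section 10.1.4: "During the infusion, continuous 3D data will be collected and two disruption-replenishment acquisitions will be performed". Section 4 gives its purpose as "to assess reproducibility of the replenishment curves analysis following microbubble destruction". The schema plans three examinations, one of them before SABR. Section 12.4 sets 20 patients, and Section 12.5 says that no sample size calculation was possible.

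The objective in Section 1.1 is wider: to "determine the feasibility and reproducibility of 3D contrast enhanced ultrasound imaging in liver cancer patients" having SABR. Sections 10.1.2 and 12.1 repeat it. On the pre/post comparison, Section 12.3 says: "Large mean differences will be indicative of treatment (SABR) effect".

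**The concern.** Three things are left open.

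- **Precision.** A label taken from a point estimate treats 20 patients as if they fixed the CCC to within one band. The moderate band is only 0.05 wide.
- **Pairs.** A pair is evidently the two acquisitions of one examination. The plan does not say whether the CCC uses baseline pairs only, each visit separately, or all visits together. Pooling visits into one CCC can raise it although measurement error is unchanged.
- **Meaning.** Two acquisitions in one infusion share the session and the contrast delivery. With only one untreated examination, nothing in the design isolates variation between sessions. A reader could take a good same-infusion result as reproducibility across visits, and then use it to judge whether a pre/post change is real.

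The estimates are also meant to help size later studies, so their precision is part of what the pilot delivers.

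**Working it through.** The plan states no precision, power or expected CCC, so there is no figure of its own to reproduce. The inputs are 20 patients (Section 12.4), three examinations each (schema), two acquisitions per examination (Sections 4 and 10.1.4), the label cut-offs, and the 80 to 90% target for successful repeat scans (Section 12.3). That target gives 0.8 × 20 = 16 to 0.9 × 20 = 18 pairs at one visit. Normal pairs with no systematic shift are an assumption.

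**1. Interval.** With z = atanh(CCC) and SE = 1/√(n − 2), the 95% limits are tanh(z ± 1.96·SE).

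| Observed CCC | 20 pairs | 16 pairs |
|---|---|---|
| 0.95 | 0.879 to 0.980 | 0.864 to 0.982 |
| 0.97 | 0.926 to 0.988 | 0.917 to 0.989 |
| 0.98 | 0.950 to 0.992 | 0.944 to 0.993 |

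At n = 20 the interval is 2 × 1.96/√18 = 0.92 wide on the z scale. The moderate band is atanh(0.95) − atanh(0.90) = 1.832 − 1.472 = 0.36 wide. The substantial band is 2.647 − 1.832 = 0.81 wide. Neither can contain the interval. The lower limit reaches 0.90 at an observed 0.959, so a substantial result is compatible with poor only between 0.95 and about 0.959.

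**2. How often the single label is wrong** (simulated normal pairs, at least 60,000 samples per value).

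| True CCC | 20 pairs | 16 pairs |
|---|---|---|
| 0.70 | 0.4% | |
| 0.80 | 4% | |
| 0.88 | 30% | |
| 0.91 | 52% | 56% |
| 0.925 | 45% | 50% |
| 0.94 | 45% | 50% |
| 0.96 | 35% | 38% |
| 0.97 | 16% | 20% |
| 0.98 | 8% | 12% |
| 0.988 | 31% | |
| 0.991 | 45% | |

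At 20 pairs, errors of two or more categories are under 3% at every value in the table (highest about 2.7%, at 0.96). They reach about 7.5% only for a true value right at 0.95, where that share of samples falls below 0.90.

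**3. All three visits.** Up to 3 × 20 = 60 pairs exist. If all were independent, an optimistic limit, the error would fall to about 18% at 0.925 and 3% at 0.97, and an observed 0.97 would have a CI of 0.950 to 0.982. With within-patient correlation ICC, the effective number is 60/(1 + 2·ICC): 30, 23 or 20 at ICC 0.5, 0.8 or 1.0.

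**4. Pooling visits into one CCC.** If visit means differ, pooled CCC = (ρ + v)/(1 + v), where v is the variance of the three visit means divided by the per-visit variance of one acquisition. Assumed shifts of 0, 0.5 and 1 SD give v = 0.167; shifts of 0, 1 and 2 SD give v = 0.667. Then 0.925 becomes (0.925 + 0.167)/1.167 = 0.936 or (0.925 + 0.667)/1.667 = 0.955. The second crosses into substantial with measurement error unchanged.

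**5. One infusion.** Section 10.1.3 gives 1.3 mL in 50 mL at up to 10 mL/min, so the infusion lasts at least 51.3/10 = 5.1 min. A 2-minute wait and two acquisitions of about 31 s take 2 + 62/60 = 3.0 min. The timing agrees with the statement that both acquisitions fall within one infusion.

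**6. Pre/post change.** The 95% half-width of a mean is t(0.975, n − 1)/√n: 2.093/√20 = 0.47 SD with 20 patients and 2.131/√16 = 0.53 SD with 16. The documents give no between-visit noise. Assuming a same-infusion CV of 10% and a between-visit CV of 0, 10 or 20%, the noise variance of a pre/post change is (10² + 0²)/10² = 1, (10² + 10²)/10² = 2 or (10² + 20²)/10² = 5 times that of a same-infusion difference, with one acquisition per visit.

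**The case against.** The strongest reply is that this is an exploratory pilot. The endpoint is estimation of the CCC, and the label is only a reading of it. Section 12.3 also plans the histogram, mean, median, variance and maximum of the repeat differences, so a reader need not rely on the label. Section 4 limits the repeats to the replenishment-curve analysis and Section 10.1.4 places them in one infusion, so the design is disclosed. Section 10.1.5 lists separate measures, so one CCC per measure is the natural reading. Preferring baseline pairs is partly a matter of choice, since the objective concerns patients undergoing SABR.

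Most of this stands, and it is why the point is minor. It does not supply an interval or name the visits, and the objectives and Section 12 still speak of reproducibility without the limit that Section 4 gives.

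A reader might infer that the label is usually wrong unless the true CCC is about 0.97 or more. That does not follow. The rule works at low values (4% wrong at 0.80, under 1% at 0.70) and fails again near 0.99 (45% wrong at 0.991). The documents give no expected CCC, so no overall error rate can be claimed.

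**Conclusion.** The point holds as a minor one. With pairs from one visit, the single label is unreliable near any cut-off and throughout the narrow moderate band, and more reliable well away from the cut-offs. Most errors are to an adjacent label. More usable pairs reduce the error rates, but by how much depends on within-patient correlation, which the documents do not give. The intervals and error rates rest on the normal, no-shift model; the visit shifts and CVs are illustrations only.

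That the result is same-infusion repeatability follows from the design and needs no model. A reader might go further and infer that reproducibility between sessions is poor, or that the pilot cannot meet its purpose. The documents support neither: between-session variation is simply not isolated, and no go/no-go decision depends on the label.

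**What to change.** In Section 12.3:

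1. Report the CCC for each perfusion measure with a 95% CI, and interpret the label in the light of that interval rather than from the point estimate alone.
2. Estimate the CCC per visit, for example with the baseline pairs as the main estimate and later visits shown separately. Do not pool visits into one CCC. Correct the pointer to Section 10.1.5.
3. Describe the result as same-infusion repeatability.
4. Give a 95% CI for the mean pre/post change at each post-SABR visit (0 to 7 days; 2 to 4 months) before reading a large mean difference as a SABR effect. Note that same-infusion variance leaves out any between-visit noise.

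The cost is a few sentences and a few intervals, with no extra scans, contrast or patients. The downside is a less definite, and possibly less favourable, reproducibility statement: at 20 pairs, an interval around any moderate or substantial result will reach at least one other band.
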